## 2.4 Endpoints

The primary endpoint is to determine per lesion sensitivity of  $^{68}\text{Ga}$  PSMA-11 for the detection of prostatic lesions in patients with elevated PSA and abnormal mp-MRI of the prostate (as defined as at least one lesion with PI-RADS v2.1 score 5 with any PSA or score 4 and PSA  $\geq 10$  ng/mL). A second endpoint will be to determine per person sensitivity of  $^{68}\text{Ga}$  PSMA-11 for the detection of metastatic disease, compared to standard of care imaging.

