### 3.1 Inclusion Criteria

- 3.1.1 Patients with suspected prostate cancer (e.g., abnormal digital rectal exam, elevated and/or rising PSA) as determined by referring physician
- 3.1.2 Patients must have had a diagnostic, standard of care mp-MRI of the prostate with at least one lesion with a PI-RADS v2.1 score  $\geq 4$
- 3.1.3 In men with PI-RADS v2.1 score 4, PSA should be  $\geq 10$  ng/mL. In men with at least one PI-RADS v2.1 score 5 lesion, there is no restriction on PSA level.
- 3.1.4 Patients must be scheduled for biopsy or radical prostatectomy
- 3.1.5 Patients must be older than 18 years of age
  
- 3.1.6 Patients should not have had any type of curative or palliative therapy for prostate cancer before enrolling in the study
- 3.1.7 Patients must be medically stable as judged by the patient's physician
- 3.1.8 Patients must be able to lie still for a total of 60 minutes for the PET/CT scans
- 3.1.9 Ability to understand and the willingness to sign a written informed consent

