### 3.2 Exclusion Criteria

- 3.2.1 Patients who have had a prior prostatectomy or radiotherapy for prostate cancer cannot participate in the study
- 3.2.2 Patients who have had a prior biopsy for prostate cancer cannot participate in the study
- 3.2.3 Patients who have been treated for cancers other than skin cancers
- 3.2.4 Subjects may not be receiving any other investigational agents for the treatment of the cancer under study
- 3.2.5 Patients may not weigh more than the maximum weight limit for the PET/CT scanner table ( $>200\text{kg}$  or 440 lbs)

---

- 3.2.6 History of allergic reactions attributed to compounds of similar chemical or biologic composition to  $^{68}\text{Ga}$  PSMA-11 or other agents used in the study such as gadolinium-based intravenous contrast agent used during the mp-MRI
- 3.2.7 Prior TURP/BPH procedures, including steam/laser therapies.

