#### **10.3 Data Analyses**

Because of the small number of subjects, descriptive statistics will be used, such as percentage of times a focus of uptake in the prostate can be seen on the PET/CT and whether this focus corresponds to any detectable abnormality on review of mp-MRI of the prostate. To be specific, we will summarize percent of incidences when 1) PET/CT is concordant with mp-MRI, 2) uptake seen on PET/CT but normal on mp-MRI and 3) no uptake on PET/CT but abnormal seen on mp-MRI. This will be displayed in a two-by-two contingency table.

Comparison will also be made to pathologic specimens from biopsy and/or prostatectomy (as reference standard) to correlate whether abnormal foci of tracer uptake correspond to sites of tumor. The per-lesion diagnostic performance of PET/CT (sensitivity and false positives) will be reported. This will be displayed in a two-by-two contingency table.

With regard to lesions outside the prostate, comparison will be made of the results from the  $^{68}\text{Ga}$  PSMA-11 scan and possible lesions seen on conventional imaging, such as pelvic CT or MRI or bone scintigraphy. To be specific, we will summarize percent of incidences when 1) PET/CT is concordant with pelvic CT/MR/BS, 2) uptake seen on PET/CT but normal on pelvic CT/MR/BS and 3) no uptake on PET/CT but lesion seen on pelvic CT/MR/BS. This will be displayed in a two-by-two contingency table.

If possible, biopsy confirmation of sites of abnormal focal  $^{68}\text{Ga}$  PSMA-11 uptake outside the prostate gland will be obtained. If biopsy is not possible due to position or size of suspected lesion, post treatment conventional imaging will be performed and results will be compared for regression in size. The per-site diagnostic performance of PET/CT (sensitivity and false positives) will be reported. This will be displayed in a two-by-two contingency table.

Agreement between two readers in continuous measurements (mean and max SUV) will be assess by intraclass correlation coefficients (ICC) and Bland-Altman plots per area of interest. Agreement between two readers in discrete measurements (visual distinguishability of primary tumor, additional primary lesion, sites of metastasis) will be assessed by Cohen's kappa.

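### The primary per-lesion sensitivity pools biopsy and whole-mount references with no split and no precedence rule, so the single figure is likely, though not certainly, too high

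*Combined protocol and SAP*

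**What the plan says.** Section 2.4: "The primary endpoint is to determine per lesion sensitivity of" the tracer for prostatic lesions. Section 10.3 holds the only analysis text for it. The reference is introduced with "Comparison will also be made to pathologic specimens from biopsy and/or prostatectomy (as reference standard", followed by "The per-lesion diagnostic performance of PET/CT (sensitivity and false positives) will be reported", shown in a two-by-two table. Neither 10.3 nor 4.3 plans a breakdown by type of reference.

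Both routes are open at entry (3.1.4): "Patients must be scheduled for biopsy or radical prostatectomy". The expected mix is not given. Under 3.2.2, "Patients who have had a prior biopsy for prostate cancer cannot participate in the study", so any biopsy follows entry. Sections 5.3 and 5.4 follow pathology for two years, so a man can be biopsied on study and operated on later.

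Section 4.3 mentions whole-mount correlation for men who have surgery with no biopsy. Its next sentence plans MRI-based molds for surgical patients without that limit. Section 9.0 accepts tissue from either procedure. No section says which reference decides when a man has both.

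**The concern.** The two references define different denominators. With whole-mount pathology, a cancer missed by PET and by mp-MRI still counts as a false negative. In a biopsy-only man it counts only if a core happens to hit it. Section 1.1 itself notes sampling error in unguided biopsy, and says that mp-MRI identified fewer than half of the individual lesions in a prostatectomy series.

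One merged number is therefore sensitivity in some men and detection among biopsy-proven cancers in others, without a label. A reader cannot tell how much rests on each. Without a precedence rule, two analysts could also compute different primary results from the same data. Section 10.2 intends the results as preliminary data for a larger PET/MRI study, so it matters what the figure estimates.

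**Working it through.** The plan states no expected sensitivity, power or derived sample size, so there is no figure of its own to reproduce. The check concerns the direction of the bias and its plausible size. **Every input below is an assumption**, except that m = 0.45 reflects the fewer-than-half statement in 1.1. That series may not match men selected for PI-RADS 4 or 5, so m = 0.70 is shown as well.

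**Model.** m is the share of cancers that mp-MRI sees. PET detects a share sM of MRI-visible and sN of MRI-invisible cancers, so true sensitivity is S = m·sM + (1−m)·sN. A share b of cancers lies in biopsy-only men. Biopsy proves a mean share v1 of PET-positive and v0 of PET-negative cancers. Whole-mount pathology is taken to find all cancers, and S is taken to be equal in both groups of men.

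Pooled = S[(1−b) + b·v1] / {(1−b) + b[S·v1 + (1−S)·v0]}

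For b > 0 and S < 1 this exceeds S exactly when v1 > v0.

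**MRI-led biopsy.** Take sM = 0.9 and sN = 0.3. Biopsy proves 90% of MRI-visible cancers and 50% or 25% of all others. For m = 0.45 and 25%:
- PET and MRI positive 0.405; MRI only 0.045; PET only 0.165; neither 0.385. S = 0.405 + 0.165 = 0.570.
- Proven PET-positive: 0.405×0.9 + 0.165×0.25 = 0.40575, so v1 = 0.71.
- Proven PET-negative: 0.045×0.9 + 0.385×0.25 = 0.13675, so v0 = 0.32.
- At b = 0.5: (0.285 + 0.202875) / (0.5 + 0.27125) = 0.633, a shift of +6.3 points.

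| m | True S | Proven, MRI-invisible | v1 | v0 | Pooled, b = 0.25 | Pooled, b = 0.5 |
|---|---|---|---|---|---|---|
| 0.45 | 57.0% | 50% | 0.78 | 0.54 | 58.6% | 60.5% |
| 0.45 | 57.0% | 25% | 0.71 | 0.32 | 59.7% | 63.3% |
| 0.70 | 72.0% | 50% | 0.85 | 0.60 | 73.3% | 74.8% |
| 0.70 | 72.0% | 25% | 0.82 | 0.41 | 74.2% | 76.8% |

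The shift is +1 to +6 points.

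**What drops out.** Losses occur on both sides. For m = 0.45 and 25%, PET-positive losses are 0.570 − 0.40575 = 0.164 out of total losses 1 − 0.5425 = 0.4575, or 36%. For m = 0.70 and 50% they are 0.108/0.22 = 49%. These missing true positives pull the figure down and partly offset the missing false negatives.

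**Larger shifts.** Suppose biopsy proves every imaging-visible cancer and half or none of the doubly missed ones. At b = 0.5, 57% reads 63% or 71%, and 72% reads 76% or 80% (+4 to +14). At b = 0.25 the shift is +2 to +6.

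**Reversals, at b = 0.5 and m = 0.45.** With sM = 0.5, sN = 0.7 and proof rates of 90% and 50%, v1 = 0.65 and v0 = 0.73, so a true 61.0% reads 59.8%. With sM = 0.9 and sN = 0.3, if biopsy proves 60% of imaging-visible and 80% of doubly missed cancers, 57.0% reads 54.4%.

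**False positives.** In the MRI-led cases, 1 − v1 = 15% to 29% of PET-positive cancers in biopsy-only men stay unproven. Scored as false positives, they would inflate that count; the plan does not say how they are scored.

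**Additional lesions (2.1.1).** The pathology-confirmed share of PET-only cancers is (1−b) + b × (proof rate). This is 0.75 + 0.25×0.5 = 0.875 at one end and 0.5 + 0.5×0.25 = 0.625 at the other. A count of unverified foci is unaffected; a pathology-confirmed count is not.

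**Precision.** Exact 95% limits, ignoring clustering of lesions within men, are 26–88% for 6/10, 36–81% for 12/20 and 41–73% for 23/40. For 23/40 (57.5%) the limits lie 16.6 points below and 15.5 above.

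**The case against.** The strongest objection is scale. This is a descriptive pilot of up to 20 men with no test and no decision threshold. Even at 23/40 the half-width is at least 15 points, more than any shift shown above, so the split will rarely demonstrate the bias. The whole-mount group is selected by the decision to operate, so its estimate is not free of bias either. All of this stands and limits the weight of the point. It does not remove it, because wide intervals do not tell a reader that two denominators have been merged.

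The biopsy-only share is also arbitrary. The documents support neither a quarter nor a half, and later surgery could make it small. At b = 0.1 the model gives only about +0.5 to +2 points, and a larger share gives more. This stands too.

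Three stronger readings are tempting but not supported:
- A reader might infer that prostate biopsies are aimed at PET foci, which would favour the larger shifts. Section 4.3 speaks of confirming PET foci where possible under standard of care, and the matching sentence in 10.3 is limited to other sites ("PSMA-11 uptake outside the prostate gland will be obtained"). PET-directed prostate biopsy is not established.
- A reader might infer that PET-negative cancers never enter the denominator in biopsy-only men. The plan tabulates findings with "no uptake on PET/CT but abnormal seen on mp-MRI", and such cancers count if biopsy proves them.
- A reader might infer that 4.3 bars whole-mount correlation for men biopsied first. Its next sentence, 9.0 and 10.3 all point to inclusion. What is missing is the precedence rule.

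**Conclusion.** The point holds as a reporting gap in the primary result. The missing split and the missing precedence rule follow from the text and need no assumption. Upward bias is likely because PET and mp-MRI tend to see the same cancers and biopsy tends to prove what imaging shows, but the documents establish neither tendency. It would be wrong to say that the pooled figure is inflated for certain.

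The +1 to +6 points are an illustration and rest on MRI-led biopsy, a biopsy-only share of a quarter to a half, PET detecting MRI-visible cancers better than invisible ones, and equal true sensitivity in both groups of men. The top of the larger range (+14) requires every PET-positive cancer to be proven and no doubly missed cancer to be found. This is a low-end change that should be made; it does not put the study's conduct or its primary endpoint in doubt.

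**What to change.** In section 10.3:
- Report per-lesion sensitivity and false positives separately for men with whole-mount pathology and men with biopsy only, with numbers of men and lesions and exact intervals.
- Label the biopsy-only figure as detection among biopsy-proven cancers.
- Show PET foci without tissue confirmation in a separate row, not as false positives.
- Note beside any pooled figure that it is likely inflated.
- State whether the additional-lesion count for 2.1.1 is of all PET-only foci or of pathology-confirmed ones.
- State that whole-mount pathology is the analysis reference for every man who has a prostatectomy, including after an on-study biopsy.

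Align the whole-mount sentence in 4.3 with 9.0 and 10.3. Record for each lesion which reference verified it.

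The cost is wording in two sections and one or two case report form fields. No procedure is added, since pathology review and the molds are already planned, and 2.4 need not change. The price is small strata with the wide intervals shown above.

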**1.4 Rationale**

A recent case report has documented that  $^{68}\text{Ga}$  PSMA-11 PET/CT may identify a prostate primary lesion even when mp-MRI does not [13]. In addition, mp- MRI may detect only a single lesion with PI-RADS v 2.1  $\geq 4$  but prostate cancer is often multifocal [3] and with the addition of  $^{68}\text{Ga}$  PSMA-11 PET/CT, those additional prostatic lesions might be identified. Several studies have demonstrated that early dynamic PET/CT imaging immediately after injection of  $^{68}\text{Ga}$  PMSA-11 can enhance primary prostate cancer detection as tumor uptake begins rapidly after injection and before the urinary bladder begins to fill with excreted tracer [7, 14].

In addition to identifying primary prostatic lesions, it is possible that  $^{68}\text{Ga}$  PMSA-11 PET/CT may be able to detect more metastatic disease than that detected on current standard of care staging imaging for patients with elevated PI-RADS scores and PSA values.  $^{68}\text{Ga}$  PMSA-11 PET/CT is reported to be able to detect small suspicious nodes and extra prostatic lesions due to its greater sensitivity and specificity compared to a variety of other imaging modalities [4, 8, 12].

The purpose of the proposed research is to evaluate the added value of  $^{68}\text{Ga}$  PSMA-11 PET/CT in relation to detect additional primary prostate cancer lesions compared to mp-MRI in a group of patients with elevated PI-RADS scores and PSA. We propose that the addition of early dynamic  $^{68}\text{Ga}$  PMSA-11 PET/CT imaging to the more usual delayed imaging will enhance detection of primary lesions and additional lesions not detected on the mp-MRI. In addition, the dynamic imaging will allow us to evaluate the kinetics of uptake in the prostate gland. It is possible that even in the absence of focal uptake, hyperemia of the gland could indicate the presence of an occult primary.

A second purpose of this research is to examine the value of  $^{68}\text{Ga}$  PSMA-11 PET/CT in this same group of patients in detecting metastatic disease at initial staging in comparison with current standard of care imaging such as CT and MRI.

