**1.5 Correlative Studies**

**2.0 N/ASTUDY OBJECTIVES**

**2.1 Primary Objectives**

- 2.1.1 To assess whether  $^{68}\text{Ga}$  PSMA-11 PET/CT can detect additional primary prostate cancer lesions through use of early dynamic PET/CT imaging in comparison to mp-MRI in patients with PI-RADS v2.1 score 5 (with any PSA), or score 4 and PSA  $\geq 10$  ng/mL.

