### 4.2 Scan Acquisition

Patients will be scanned on a 128 slice PET/CT scanner. The patient will be positioned supine, with arms elevated above the head as tolerated by the patient. Data acquisition will occur as 2 discrete components: 1) a dynamic part (dPET/CT studies) and the static part (whole-body PET/CT). With the patient on the scanning table, the patient will be injected with  $^{68}\text{Ga}$  PSMA-11 and dPET/CT scanning will be performed over the pelvic area for 30 minutes [11, 12, 16]. The dPET/CT will be obtained in list mode with dynamic frames acquired at 10 x 30 seconds, 5 x 60 seconds, 5 x 120 seconds and 2 x 300 seconds. At 60 minutes post injection, a standard whole body PET scan with images from vertex of the skull to the feet will be acquired at 2-3 minutes per bed step, adjusted for body weight, along with CT images over the same range. The manufacturer's CT dose exposure limit software will be utilized. CT data will be used for attenuation correction and for anatomic localization of uptake sites [15]. The CT data will be reconstructed with soft tissue (B40f) and bone (B80) kernels.

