### 4.3 Imaging Analysis

For the dynamic scan, all frames will be summed to produce a single image over the pelvis. This image will be visually evaluated for focal uptake in and around the prostate gland. In addition, the dynamic image frames will also be used to construct time activity curves comparing post injection time vs standard uptake value (SUV) of  $^{68}\text{Ga}$  PSMA-11 uptake. These curves will be constructed with volumes of interest in the prostate as a whole, in any visible focal prostate lesions and over the common left iliac artery to provide an arterial input curve. If metastatic lesions are detected on this scan, separate time activity curves will be calculated as well.

Whole body images will be visually and quantitatively evaluated independently by two experienced PET/CT readers. The readers will first assess whether the primary tumor is visually distinguishable from the surrounding prostate tissue. A prostate tumor will be judged positive if the focal tracer uptake is higher than that of the surrounding prostate tissue. For calculations of SUV, a VOI will be drawn around areas of focal uptake within the prostate using iso-contour (SUVmax). The same size VOI will be drawn in the region of the uninvolved prostate. If no focal uptake is seen in the prostate, a VOI will be drawn around the prostate.

Comparisons will be made between the interpretations provided by the two PET/CT readers and the degree of agreement will be calculated. Mean and maximum SUVs will

---

be obtained on all areas of interest. Anatomic measurements of suspicious lymph nodes will be made in the short axis.

To evaluate focal uptake in lymph nodes and distant metastatic disease, VOIs will be drawn around each lesion. SUV maximum and mean will be recorded for all lesions. In addition, VOIs will be drawn around normal uptake in the prostate and a 2 cubic centimeter VOI will be drawn in the gluteal muscle, for use as normal background [7]. A lesion will be considered positive when the uptake exceeds normal background.

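### The primary objective names early dynamic PET/CT, but the endpoint and the listed prostate tables use one undivided PET/CT result, so they cannot show which additional lesions the dynamic scan contributed

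*Combined protocol and SAP*

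**What the plan says.** - **Objective and rationale.** Section 2.1 asks whether the tracer's PET/CT "can detect additional primary prostate cancer lesions through use of early dynamic PET/CT imaging in comparison to mp-MRI". Section 1.4 gives the mechanism, that early imaging "can enhance primary prostate cancer detection as tumor uptake begins rapidly after injection and before the urinary bladder begins to fill with excreted tracer". It then states the hypothesis as an increment: adding the early dynamic scan "to the more usual delayed imaging will enhance detection of primary lesions and additional lesions not detected on the mp-MRI".
- **Acquisition.** Section 4.2 states: "Data acquisition will occur as 2 discrete components". One is a 30-minute dynamic pelvic scan starting at injection. The other is a whole-body scan at 60 minutes.
- **Reading.** Section 4.3 sums the dynamic frames into one image and adds: "This image will be visually evaluated for focal uptake in and around the prostate gland". For the other component it says: "Whole body images will be visually and quantitatively evaluated independently by two experienced PET/CT readers". The positivity rule (focal uptake above that of the surrounding prostate) is worded generally but stands in the whole-body paragraph. The number of readers for the dynamic image is not given.
- **Endpoint.** Section 2.4 reads "The primary endpoint is to determine per lesion sensitivity of" the agent for prostatic lesions. It names neither scan.
- **Analysis.** Section 10.3 sets PET/CT against mp-MRI in three categories, then against pathology, where "The per-lesion diagnostic performance of PET/CT (sensitivity and false positives) will be reported". Cohen's kappa is planned for the discrete readings. Section 10.3 does not mention the dynamic scan.

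**The concern.** The only primary objective credits additional lesions to one component of the examination, and the rationale expects that component to add to the other. Both components are acquired and both are looked at. After that the distinction disappears: the endpoint and the prostate tables listed in 4.3 and 10.3 refer simply to PET/CT, and no section says how two reads become one result.

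A team that follows the plan exactly could therefore report how well the examination performs and still be unable to say which additional lesions came from the dynamic scan. It would also have to decide, after the images are read, what counts as a positive PET/CT when the two images disagree.

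**Working it through.** The documents give no alpha, power, effect size or lesion count, so there is no planned figure to reproduce. The check is mainly one of structure, followed by an illustration.

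**1. Tracing the dynamic scan through the plan**

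| Step | Section | Dynamic scan separate? |
|---|---|---|
| Hypothesis | 1.4 | Yes, as a gain over delayed imaging |
| Primary objective | 2.1 | Yes, compared with mp-MRI |
| Acquisition | 4.2 | Yes |
| Reading | 4.3 | Yes, but no stated number of readers |
| Primary endpoint | 2.4 | No |
| Table against mp-MRI | 4.3, 10.3 | No |
| Table against pathology | 10.3 | No |
| Kappa | 10.3 | Image not stated |

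**2. Two ways to read the single PET/CT result**

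- *Whole examination.* This is the natural reading. Sections 6.0 and 10.1 treat the tracer examination as the thing under study, and 4.3 has the dynamic image read for uptake in the prostate. A proven lesion seen only at 60 minutes then counts the same as one seen only on the dynamic image.
- *60-minute read only.* This is possible because two independent readers are expressly named only for the whole-body images. Lesions seen only on the dynamic image would then drop out.

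**3. What the planned table can distinguish**

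The counts here are assumptions: 30 proven lesions, 18 seen on both images, 6 on neither, and 6 on one image only. Whole-examination sensitivity is (both + dynamic only + delayed only) / 30.

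| Dynamic only | Delayed only | Whole examination | Lesions gained over 60-minute read |
|---|---|---|---|
| 6 | 0 | (18 + 6 + 0)/30 = 80% | 6 |
| 3 | 3 | (18 + 3 + 3)/30 = 80% | 3 |
| 0 | 6 | (18 + 0 + 6)/30 = 80% | 0 |

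The 80% is a correct result for the examination in every row. The last column, which bears on the hypothesis in 1.4, cannot be recovered from it.

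**4. What a breakdown could show with 20 patients**

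Take the proportion of patients with at least one proven lesion gained from the dynamic image. Exact (Clopper-Pearson) 95% intervals are:

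- 0/20: 0% to 16.8%
- 3/20: 3.2% to 37.9%
- 6/20: 11.9% to 54.3%

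The chance of seeing at least one such patient in 20 is 1 − (1 − p)^20:

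- p = 5%: 1 − 0.95^20 = 64%
- p = 10%: 1 − 0.90^20 = 88%
- p = 15%: 1 − 0.85^20 = 96%

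These chances assume that all 20 patients are evaluable and every such lesion is verified. If only half of these patients were verified (an assumption), p is halved and the chances become 1 − 0.975^20 = 40%, 1 − 0.95^20 = 64% and 1 − 0.925^20 = 79%.

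**The case against.** The strongest reply is that the objective's comparator is mp-MRI, not delayed PET/CT. No objective or endpoint commits the study to a dynamic-versus-delayed contrast; that increment appears only in the rationale. If the whole examination is the index test, the tables against mp-MRI and pathology do answer whether the examination finds additional lesions. This stands, and it limits the point to a missing breakdown rather than an invalid endpoint. It does not remove the point, because dynamic PET/CT against mp-MRI is not tabulated either.

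A second reply is that this is a descriptive pilot whose summaries are introduced as examples, and that 4.3 already calls for a visual read of the dynamic image and time-activity curves over visible prostate lesions. Some component-level information should therefore exist. That is fair. But 10.3 goes on to list specific categories, all for undivided PET/CT, and the curves describe kinetics without being linked to lesion detection. Permission to report something is not a specified record and table.

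Third, verification is incomplete. Patients may have biopsy only (3.1), and biopsy of uptake sites is obtained only where possible (4.3). This stands, and it lowers the yield of any breakdown.

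**Conclusion.** The point holds as a gap in what is recorded and tabulated. On the natural reading, the planned sensitivity and the mp-MRI comparison are valid for the examination as a whole, but the listed outputs cannot show which additional lesions the dynamic scan contributed. The rule for combining the two reads is unstated, and so is the image that the kappa covers. No numerical size can be drawn from the documents; the lesion counts above are illustrative.

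Four stronger conclusions are tempting but not supported:

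- *The reported sensitivity would be wrong by up to 20 percentage points.* In the example, a 60-minute-only endpoint would give 18/30 = 60%, 21/30 = 70% or 24/30 = 80% instead of 80%. That gap exists only under the weaker reading, which no section states.
- *The comparison is lost for good unless planned now.* The dynamic images are acquired and read in any case. Other readers, or the same readers after a washout, could score them later.
- *The next study depends on whether dynamic imaging is worth keeping.* Section 10.2 says the data are to support a larger study of hybrid PET/MRI and names no such decision.
- *The kappa certainly uses a single PET/CT result.* This is an inference from 4.3, which names two readers only for the whole-body images.

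This is a cheap improvement.

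**What to change.** Amend 4.3 and 10.3 as follows.

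1. State that the combined dynamic plus 60-minute read is the primary PET/CT result and the one used for the kappa. Apply the existing positivity rule to both images.
2. Have the same two readers score and lock the 60-minute image first. They then view the summed dynamic image, record for each lesion whether it is visible there, and score the combined read. A separate dynamic-alone session by these readers is not needed; if one is held, label it as subject to recall.
3. Report descriptively, against mp-MRI and pathology, the proven lesions gained and the false positives added by the combined read over the locked 60-minute read. Show separately the gained lesions that mp-MRI missed.
4. Give counts for lesions. Give an exact interval only for the per-patient proportion with at least one such proven lesion, among patients with pathology. Lesions within a patient are not independent, so an exact binomial interval on lesions would be too narrow if their results are positively correlated.

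**Cost.** The change needs wording, added case-report-form fields and modest reading time. Two scored reads by two readers in 20 patients is 2 × 2 × 20 = 80. The plan already implies 2 × 20 = 40 whole-body reads plus 20 to 40 dynamic reads (one or two readers), so 60 to 80 in all. The extra is about 0 to 20 reads. No new scan, patient, reader or procedure is required. The limitation to state is low precision, and lower still where dynamic-only lesions cannot be verified.
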